1 INTRODUCTION

1.1 Background

Heart failure (HF) is a serious condition with high rates of morbidity and mortality. HF is not an isolated condition, but rather the terminal phase of cardiovascular disease progression. Nearly all cardiac disorders—including myocardial infarction, cardiomyopathy, and hemodynamic overload—inevitably culminate in heart failure. Although therapeutic approaches such as pharmacotherapy, interventional procedures, and surgical interventions have seen continuous refinement in recent decades, they remain limited to symptom management rather than full functional restoration of cardiac performance. Consequently, the treatment of heart failure persists as one of medicine's most formidable global challenges.

Myocardial infarction, the most prevalent cardiac disorder, stands as a frequent precursor to heart failure. Mature cardiomyocytes are generally regarded as terminally differentiated cells with negligible regenerative capacity. Consequently, preserving and augmenting functionally competent myocardial cells emerges as the most rational therapeutic approach for various cardiac injuries. With advancing understanding of stem cell biology, harnessing their differentiation potential to regenerate cardiomyocytes, repair damaged myocardial tissue, and restore cardiac function has emerged as a promising novel strategy in contemporary heart failure treatment.

1.1.1 The mechanisms of cardiovascular regeneration

Traditionally, cardiac cells have been regarded as terminally differentiated and incapable of self-proliferation or repair^[1-3]. Although some studies suggest the existence of cardiomyocyte turnover in adult human hearts, these findings remain unverified. Indeed, the regenerative capacity of the adult mammalian heart is profoundly limited^[4]. When acute cardiac injury or chronic myocardial remodeling occurs, the substantial loss of cardiac cells far exceeds the heart's minimal intrinsic regenerative potential. This starkly contrasts with the robust cardiac regenerative abilities observed during embryonic development and in certain other species. For instance, in mammals, cardiomyocytes maintain vigorous mitotic activity throughout embryogenesis and the early postnatal period. However, this proliferative capacity rapidly diminishes thereafter, with mitotic activity becoming undetectable—lending credence to the conventional view that the adult heart consists of non-regenerative, terminally differentiated cells.

1.1.2 Cardiovascular Regeneration Therapeutics

Products in the field of cardiovascular regeneration can be categorized based on their regenerative strategies into: i) Exogenous regenerative products, which involve transplanted cells or tissues to replace damaged or dysfunctional cardiac structures; and ii) Stimulatory factors that activate endogenous regenerative mechanisms.

Stem cells, as the body's primordial cells, serve as the foundation for all tissues and organs. Stem cell therapy aims to repair diseased cells or reconstruct functional tissues, offering a fundamental treatment for numerous diseases. Consequently, leveraging their self-renewal and multipotent differentiation capabilities to treat heart failure has become a global research focus. Stem cells can be classified into skeletal myoblasts, bone marrow mononuclear cells, hematopoietic stem cells, mesenchymal stem cells, and pluripotent stem cells. Pluripotent stem cells possess unlimited proliferative and differentiation potential, including embryonic stem cells (ESCs) and induced pluripotent stem cells (iPSCs). ESCs, derived from the inner cell mass of blastocysts, hold significant promise in regenerative medicine. However, their application is constrained by ethical concerns, immune rejection, and limited source availability. In 2006, the Japanese scientist Yamanaka and his team^[5] pioneered a breakthrough by introducing four pluripotencyassociated transcription factors (Oct3/4, Sox2, c-Myc, and Klf4) into mouse embryonic fibroblasts via retroviral vectors, generating cells resembling ESCs with self-renewal and multipotent differentiation capabilities. These reprogrammed somatic cells, termed iPSCs, circumvent the ethical and immunological challenges of ESCs, providing an invaluable tool for disease modeling and drug development. With advancements in culture conditions and reprogramming efficiency, iPSCs can now be derived from various somatic cells (e.g., skin fibroblasts, peripheral blood cells) across species. They can proliferate and differentiate into diverse cell types, including cardiomyocytes^[6] — representing a key exogenous regenerative product. Within cardiac regenerative medicine, exogenous products encompass in vitro-differentiated cardiac cells, cardiovascular and endothelial progenitor cells, bioengineered cardiac tissues, and electromechanically functional vascular patches. Recent research has validated numerous approaches, some even demonstrating efficacy in primate models^[7–9].

1.1.3 Preclinical and Clinical Research in Cardiac Regeneration

In pioneering studies on pluripotent stem cells, Laflamme et al. [10] successfully transplanted heat shock-treated human embryonic stem cell-derived cardiomyocytes (hESC-CMs) into the left ventricular wall of healthy athymic rats. The transplanted cells demonstrated excellent survival rates, with the majority exhibiting robust expression of myosin heavy chain (MHC). Notably, the hESC-CMs significantly induced angiogenic responses, accompanied by substantial neovascularization in the transplantation Echocardiographic and magnetic resonance imaging (MRI) assessments revealed ameliorated ventricular dilation four weeks post-transplantation. Subsequent research by Van Laake et al.[11] involved transplantation of hESC-CMs into myocardial infarction models using NOD SCID mice. The study documented progressive enrichment and maturation of cardiomyocytes, with MRI data indicating marked cardiac functional improvement at four weeks, though this beneficial effect diminished by three months posttransplantation. More recently, Chong et al.[8] made the groundbreaking discovery that hESC-CMs could regenerate cardiac tissue in large non-human primates. Their transplantation into infarcted monkey hearts 14 days post-myocardial infarction resulted in successful regeneration of the damaged myocardial regions. The latest findings by Zhu et al. [12] further demonstrated that transplantation of hESC-derived cardiovascular progenitor

cells in non-human primates led to significant enhancement of left ventricular ejection fraction within 28 days post-intervention.

Induced pluripotent stem cell (iPSC) technology offers a promising alternative by circumventing immunological rejection and ethical or religious controversies. The application of iPSCs in myocardial tissue repair and cardiac functional restoration has opened new therapeutic avenues for heart failure treatment. Miki et al.[13] engineered myocardial sheets from murine iPSCs using in vitro tissue engineering techniques and transplanted them into rats with chronic myocardial infarction. Histological analysis confirmed the survival of the transplanted myocardium at the epicardial site four weeks post-transplantation. Compared to the control group, the transplanted group exhibited significant improvements in cardiac function and attenuation of left ventricular remodeling. Higuchi et al.[14] introduced red fluorescent protein-labeled murine iPSC-derived cardiomyocytes into infarcted rat hearts. Functional assessments revealed progressive enhancement of left ventricular ejection fraction beginning three days post-transplantation. By two weeks, the engrafted cardiomyocytes expressed cardiac myosin and connexin 43 on the cardiac surface. Kawamura et al. [15] demonstrated that transplantation of humanderived regenerated cardiomyocytes into pigs with ischemic cardiomyopathy substantially improved cardiac function, mitigated left ventricular remodeling, and maintained detectable cell survival for eight weeks without teratoma formation. Recent advances in tissue engineering have further expanded therapeutic possibilities. Weinberger et al. [16] reported that iPSC-based artificial cardiac tissue transplantation restored cardiac function in guinea pigs with myocardial injury. Similarly, Gao et al. [17] found that human-derived engineered myocardial patches significantly enhanced left ventricular function, reduced infarct size, attenuated myocardial hypertrophy, and reversed infarction-associated alterations in striated muscle actin-regulated protein phosphorylation in a porcine myocardial infarction model. A landmark 2016 study published in Nature demonstrated that allogeneic iPSC-derived cardiomyocytes achieved robust electrical and mechanical coupling with host myocardium, successfully regenerating cardiac tissue in non-human primates.[18]

With the continuous advancement of preclinical research, clinical studies exploring stem cell-based regenerative therapies for heart failure have progressed rapidly. The first clinical trial in this field was conducted in 2002 to evaluate the potential of stem cells in preventing heart failure^[19]. Assmus et al.^[20] demonstrated significant improvement in left ventricular ejection fraction (LVEF) among 103 heart failure patients following intracoronary infusion of autologous bone marrow mononuclear cells. Similarly, a Phase I clinical trial involving percutaneous trans-coronary-venous delivery of autologous skeletal myoblasts showed LVEF improvements of 3-8% in 6 out of 9 treated patients^[21]. The landmark SCIPIO trial revealed that transplantation of autologous c-kit+ cardiac stem cells substantially enhanced left ventricular function while reducing infarct size^[22]. Further supporting these findings, the PROMETHEUS randomized controlled trial demonstrated that mesenchymal stem cell therapy in ischemic heart failure patients led to improved LVEF and reduced scar tissue formation in surgical patients^[23]. These clinical trials collectively underscore the promising therapeutic potential of stem cell-based approaches as a novel treatment paradigm for heart

Protocol (version 6.1)

Version data: 2021.08.01

Confidential
Page 13 of 38

failure. A pivotal milestone was achieved in 2015 when [name] team published the first human clinical trial of pluripotent stem cell-derived cardiac cells in the European Heart Journal^[24]. Subsequent reports confirmed the therapeutic potential of hESC-derived cardiovascular progenitor cells in treating severe ischemic left ventricular dysfunction. Six patients (mean age 66.5 years, baseline LVEF 26%) exhibited marked improvement in systolic function post-transplantation, with no observed arrhythmias or tumor formation during long-term follow-up^[25].

Through systematic literature review, we have identified that stem cell therapy has been predominantly investigated for ischemic heart disease treatment. Current research efforts encompass over 100 clinical trials targeting acute myocardial infarction and more than 90 studies focusing on chronic ischemic heart failure (see Table 1 for comprehensive summary). Our analysis included 48 systematic reviews and meta-analyses^[26], all demonstrating remarkable consistency in supporting the feasibility and safety of stem cell-based interventions. These studies collectively report significant improvements in both cardiac function and clinical parameters among patients with acute myocardial infarction and chronic ischemic left ventricular dysfunction. In conclusion, cardiac regenerative therapy has been conclusively established as an effective, feasible, and safe therapeutic strategy for patients with ischemic heart disease. The substantial body of clinical evidence underscores its potential as a transformative treatment modality in cardiovascular medicine^[27].

Table 1. Summary of Randomized Clinical Trials in Cardiovascular Regenerative Medicine

Disease Classification	Regenerative Product	Safety Profile	Overall Efficacy
Acute Myocardial Infarction	BMMNC[28-38]	Safe	Neutral
(n=2732)	BM-MSC[39]	Safe	Neutral
(ii 2732)	Specific BM Cells[40-42]	Safe	Neutral
	ADSC[43]	Safe	Neutral
	CDC[44]	Safe	Positive
Ischemic Heart Failure	SM[45-48]	Safe	Neutral
(n=2035)	BMMNC[49-52]	Safe	Neutral
	BM-MSC[53, 54]	Safe	Positive
	Specific BM Cells[20, 55-60]	Safe	Positive
	CSC[61]	Safe	Positive

	Gene therapy[62-64]	Safe	Neutral
Refractory Angina	BMMNC[65-68]	Safe	Positive
(n=353)	Specific BM Cells[69-71]	Safe	Positive
	ADSC[72]	Safe	Positive
Non-Ischemic Heart Failure	BMMNC[73]	Safe	Neutral
(n=166)	Specific BM Cells[74, 75]	Safe	Neutral
	BM-MSC[76]	Safe	Neutral
Peripheral Artery Disease	BMMNC[77]	Safe	Positive
(n=1217)	Specific BM Cells[78, 79]	Safe	Positive
	Gene therapy[80, 81]	Safe	Neutral

1.2 Study Rationale

Extensive large-animal studies on post-myocardial infarction heart failure have demonstrated that direct transplantation of exogenous cardiomyocyte products can reverse left ventricular remodeling and enhance systolic function, as evidenced in numerous acute and chronic models. Pluripotent stem cell-derived cardiomyocytes show promise in delaying the progression of post-infarction heart failure, offering new therapeutic prospects. Large-animal experiments reveal that allogeneic transplantation of terminally differentiated iPSC-derived cardiomyocytes with physiological cardiac function following infarction-induced heart failure enables effective electromechanical coupling with host cardiomyocytes. This intervention has been shown to improve cardiac function in treated subjects^[18]. Our research team has also validated the therapeutic efficacy of human-derived regenerative cardiomyocytes in cynomolgus monkeys. Echocardiographic and magnetic resonance imaging analyses demonstrated significant functional improvement in treated groups compared to untreated controls. Histopathological staining revealed markedly reduced infarct size and fibrosis in the intervention group. Additionally, electrocardiographic monitoring detected no malignant arrhythmic events in either the cell therapy or cell-plus-medium treatment groups during the observation period. Biochemical analyses confirmed no significant hepatic or renal dysfunction in these cohorts. While primate studies using human-derived regenerative cardiomyocyte transplantation have yielded promising results for heart failure treatment, further investigation is required to translate these findings to human clinical applications. Our team has systematically reviewed, synthesized, and developed the current experimental protocol

Protocol (version 6.1)

Version data: 2021.08.01

Confidential
Page 15 of 38

based on eight years of closely related clinical research (Table 1: Summary of Randomized Clinical Trials in Cardiovascular Regenerative Medicine).

Notably, in March 2019, Japan initiated the world's first clinical trial using induced pluripotent stem cells (iPSCs) for heart failure treatment. [name] team at Osaka University's Department of Cardiovascular Surgery received approval from the Ministry of Health, Labour and Welfare for this groundbreaking study - marking Japan's second application of iPSC-derived cell therapy since the pioneering 2014 retinal cell trial. Preliminary experimental treatment in three cardiomyopathy patients demonstrated favorable safety profiles. This clinical investigation will primarily evaluate therapeutic efficacy through a one-year validation period. These developments provide objective scientific rationale for our current trial.

2 OBJECTIVES AND ENDPOINTS

2.1 Study Objective

To evaluate the safety and efficacy of intramyocardial injection of Allogenic Human Induced Pluripotent Stem Cells-derived Cardiomyocytes in patients with severe chronic ischemic heart failure with coronary artery bypass grafting indications.

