9.3 Investigator and Responsibilities	
9.4 Informed Consent Process	30
10 REFERENCES	31

PROTOCOL SYNOPSIS

Title	Epicardial Injection of Allogeneic Human Pluripotent Stem Cell-derived Cardiomyocytes to Treat Severe Chronic Heart Failure
Sponsor	HELP Therapeutics Co., Ltd. Nanjing, China
Objective	To evaluate the safety and efficacy of intramyocardial injection of Allogenic Human Induced Pluripotent Stem Cellsderived Cardiomyocytes in patients with severe chronic ischemic heart failure with coronary artery bypass grafting indications.
Principal Investigator	[name]
Institution	Nanjing Drum Tower Hospital
Indication	Severe Chronic Ischemic Heart Failure
Study Phase	Exploratory
Study Design	single-center, open-label, randomized controlled trial
Study Population	Patients with severe chronic ischemic heart failure with definitive coronary artery bypass grafting (CABG) indications.
Sample Size	20
Treatment Groups	This exploratory trial will enroll 20 patients with severe chronic ischemic heart failure who meet the inclusion/exclusion criteria. After providing informed consent, subjects will be randomized into two groups:
	Control Group (n=10): Patients will undergo standardized coronary artery bypass grafting (CABG) alone.
	Cell Therapy Group (n=10): Patients will receive CABG followed by intramyocardial cell therapy (2×10^8 cells). Following the completion of graft anastomoses, human-derived regenerative cardiomyocytes will be administered via 10 targeted injections into the peri-infarct region.
Follow-Up Schedule	Patients will undergo three scheduled visits at postoperative intervals of 1, 6, and 12 months. During each visit, relevant clinical documentation and laboratory test results will be recorded. Following the completion of the study follow-up period, subjects will transition into post-study safety surveillance, which will continue until either mortality or loss to follow-up occurs.

Primary Endpoints	Safety:					
	1. Incidence of sustained ventricular tachycardia (1~6 Month Post-operation)					
	O Defined as the proportion of patients experiencing ventricular tachycardia lasting more than 30 seconds					
	2. Incidence of newly formed tumors (12 Month Post-operation)					
	O By comparing chest, abdominal and pelvic CT scan and PET-CT scan					
Secondary Endpoints	Safety:					

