3 STUDY DESIGN

This is a single-center, open-label, randomized controlled trial involving 20 eligible subjects who meet the inclusion/exclusion criteria. Subjects will be randomly allocated in a 1:1 ratio into two groups:

- Control Group: Standard CABG treatment only
- Cell Therapy Group: CABG + cellular transplantation (dose: 2 × 10⁸ cells) + perioperative immunosuppressive therapy

Postoperative Management:

All patients will undergo rigorous perioperative monitoring (within the first postoperative month) with comprehensive contingency protocols in place.

Follow-Up & Assessments:

Both groups will undergo identical follow-up evaluations at 1, 6, and 12 months, including:

Protocol (version 6.1)

Version data: 2021.08.01

Confidential
Page 17 of 38

Imaging studies (as per protocol), Laboratory investigations, Functional assessments. Documentation will be maintained via case report forms (CRFs) to ensure accurate and reliable data acquisition.

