4 STUDY TREATMENT

4.1 Treatment and dosage

4.1.1 Treamtment

All enrolled subjects will undergo standardized coronary artery bypass grafting (CABG) in accordance with established clinical guidelines. For patients in the cell therapy group, the treatment protocol incorporates myocardial cell transplantation alongside the standard CABG procedure. Following completion of graft anastomoses, a total of 2×10^8 allogeneic human regenerative cardiomyocytes are administered via epicardial injection at 10 sites surrounding the infarcted myocardial region.

Patients in the Cell therapy group were administered the following immunosuppressive regimen: intravenous immunoglobulin (2.5 g, IV) on preoperative day 1, intraoperative day (IOD), and postoperative day (POD) 3, combined with methylprednisolone (500 mg, IV) on preoperative day 1; rituximab (20 mg, IV) on IOD and POD4 to target CD20+ B-cell depletion; oral tacrolimus started preoperative day 3 and dose-adjusted to maintain trough levels within the target range of 3-5 ng/mL, as monitored by blood drug concentration until POD28, concurrently with mycophenolate mofetil (1 g, orally on preoperative day 1, increasing to 1.5 g/day until POD28) and prednisone (20 mg/day started IOD until POD28). The Control group did not receive any immunosuppressive medications. All study subjects

Protocol (version 6.1)

Version data: 2021.08.01

Confidential
Page 19 of 38

undergo intensive postoperative monitoring in the ICU with comprehensive emergency protocols implemented as needed.

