4.1.2 Dosage form and dosage

Cell Type: Allogeneic human regenerative cardiomyocytes

[figure not shown]
Dosage: A total of 2×10^8 cells are administered via intramyocardial injection, divided equally across 10 sites (250–500 µL per injection).

Administration: The procedure is performed intraoperatively following completion of graft anastomoses during CABG.

Control Group receive standardized CABG alone.

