6 STATISTICAL CONSIDERATIONS

6.1 Study Design

This is a single-center, open-label, randomized controlled trial. Study objective is To evaluate the safety and efficacy of intramyocardial injection of Allogenic Human Induced Pluripotent Stem Cells-derived Cardiomyocytes in patients with severe chronic ischemic heart failure with coronary artery bypass grafting indications. The sample size for this study is 20.

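### The objective credits safety and efficacy to the cell injection alone, but the two arms also differ by a six-agent immunosuppressive regimen, so the comparison answers only for the combined strategy

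*Protocol*

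**What the plan says.** The objective appears three times (synopsis, section 2.1, section 6.1) and each time names only the cells. Section 2.1 reads "To evaluate the safety and efficacy of intramyocardial injection of Allogenic Human Induced Pluripotent Stem Cells-derived Cardiomyocytes in patients", followed by the description of the population. Section 6.1 repeats it: "Study objective is To evaluate the safety and efficacy of intramyocardial injection".

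The arms are described differently in different places:

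- **Synopsis, Treatment Groups.** For the cell arm: "Patients will receive CABG followed by intramyocardial cell therapy", followed by the dose and the injection sites. Immunosuppression is not mentioned.
- **Section 3.** The cell arm is CABG, cells and "perioperative immunosuppressive therapy". The other arm is "Control Group: Standard CABG treatment only".
- **Section 4.1.1.** The cell arm receives intravenous immunoglobulin, methylprednisolone, rituximab, tacrolimus, mycophenolate mofetil and prednisone. Then: "The Control group did not receive any immunosuppressive medications".
- **Section 4.1.2.** "Control Group receive standardized CABG alone". No vehicle or sham injection is described.

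Section 8 lists the adverse effects of the immunosuppressants as a risk of their own, beside the risks of the cells. Section 8.3 gives those effects drug by drug and limits the therapy to one month. No section states that the between-arm comparison estimates the effect of a combined strategy.

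**The concern.** An objective tells the reader what a difference between arms will be taken to mean. Here it points to the cell injection, while the arms differ in three things: the cells, the act of injecting them, and the drug regimen. A reader of the synopsis alone would not know about the third.

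The gap bears on safety, which is where the primary endpoints lie. Section 8.3 names infection, hyperglycaemia, leukopenia, renal impairment or raised creatinine, and abnormal liver tests as effects of the drugs. Some of these would show in the biochemistry scheduled for the first month. Section 4.1.1 gives rituximab expressly to deplete B cells, so a low PRA or DSA at month 1 could not be read simply as low immunogenicity of the cells. If the objective stands as worded, an early excess of creatinine rises invites attribution to the product, and an early absence of antibodies invites credit to it. The design supports neither reading.

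**Working it through.** No sample-size or power figure is at issue. Section 6.3 gives 10 + 10 = 20 as an exploratory number, and the sum agrees. The check compares the arm definitions, then sets the drug dates against the endpoint windows.

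**1. What differs between the arms (sections 3, 4.1.1, 4.1.2)**

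| Component | Cell arm | Control arm |
|---|---|---|
| CABG | 10/10 | 10/10 |
| Injection procedure | 10/10 | 0/10 |
| Cells | 10/10 | 0/10 |
| Immunosuppressive regimen | 10/10 | 0/10 |

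These are exposures as assigned. Two arms yield one contrast:

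D = (CABG + injection + cells + drugs) − (CABG) = joint effect of injection, cells and drugs, including any interaction.

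The last three rows are identical, so the between-arm contrast cannot divide D among them at any sample size.

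**2. How long each drug is given (section 4.1.1)**

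| Agent | Last scheduled day |
|---|---|
| Methylprednisolone | preoperative day 1 |
| Intravenous immunoglobulin | POD3 |
| Rituximab | POD4 |
| Tacrolimus | POD28 |
| Mycophenolate mofetil | POD28 |
| Prednisone | POD28 |

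So 3 of 6 agents continue to POD28 and 3 of 6 end by POD4. Dosing covers about 28/365 = 7.7% of the postoperative year. That is a share of dosing days. It does not measure how long the drugs act.

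**3. Which endpoints fall in that period (sections 2.2 and 5.2, Table 3)**

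- *Biochemistry:* D1-D7, D14, D21, M1, M6 and M12. The first three of these six postoperative columns lie wholly within dosing. M1 has a window of ±7 days. Counting a month as 30 days (an assumption), that is day 30 − 7 = 23 to day 30 + 7 = 37, so the sample may be taken on or off drug.
- *Immunoglobulins:* listed in section 2.2.2, and section 8.3 promises their monitoring during dosing. Table 3 has no row of that name.
- *PRA/DSA:* Table 3 has M1, M6 and M12. Only M1 can coincide with dosing.
- *Perioperative SAEs and ECG monitoring:* the protocol treats the perioperative period as the first month, which is almost entirely the dosing period.
- *Sustained ventricular tachycardia, months 1 to 6:* begins about when dosing ends.
- *Tumours at 12 months; imaging, walk test, NYHA and MLHFQ at 6 and 12 months:* after dosing.

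The overlap is thus heavy for early safety results and slight for the primary and efficacy endpoints. The documents do not show that drug effects end with dosing. B-cell depletion is the plainest case where they might not.

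**The case against.** The strongest reply is that nothing is hidden. Section 3 defines the cell arm with immunosuppression, section 4.1.1 gives the regimen, and section 8.3 explains that it serves to prevent rejection of the graft. On that view it belongs to allogeneic cell therapy, and naming only the product in the objective is ordinary shorthand. This stands in part: the treatment need not change and no third arm is needed. But if the drugs are part of the therapy, the objective and the synopsis should say so, and at present they disagree with section 3.

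A second reply is timing, and it largely stands. A reader might infer that the primary endpoints and the 6- and 12-month efficacy results are equally affected. The dates in sections 2.2 and 4.1.1 do not support that, and PRA/DSA are repeated at 6 and 12 months.

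Other strong readings also go beyond the text:

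- *That every difference will be reported as a cell effect.* The protocol does not say this; it is an inference from the objective. Section 8 separates drug risks from cell risks, section 6.5.3 counts adverse drug reactions, and section 8.1 plans histopathology to trace the origin of a new tumour. That last step attributes single cases and does not separate the arm effects.
- *That blood count, procalcitonin and infection are affected endpoints.* Table 3 schedules blood count and procalcitonin at baseline only, although section 8.3 promises haematological monitoring during dosing. Infection is not among the SAEs named in section 2.2.2, whose list is open-ended.
- *That the cells' share of a difference lies between 0% and 100%.* If cells and drugs act in opposite directions, the share can be negative or exceed 100%.
- *That early differences should be put down to the drugs.* This contradicts the aliasing argument and could hide a signal from the product.

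Finally, onset windows for tables often sit in a statistical analysis plan, which is not at hand. That is fair for the table layout. The objective and the arm description are protocol content.

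**Conclusion.** The point holds as a mismatch between the stated objective and what the design identifies. The comparison estimates CABG plus cell injection with perioperative immunosuppression versus CABG alone. Cells, injection and drugs are fully aliased (10/10 versus 0/10), and a larger trial with the same two arms would not change that.

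The consequence is greatest for biochemistry, immunoglobulins, perioperative SAEs and month-1 PRA/DSA. It is limited for ventricular tachycardia at months 1 to 6, tumours at 12 months and efficacy at 6 and 12 months, subject to carry-over that the documents neither show nor exclude. The wording should be corrected, but this is no reason to redesign the trial.

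Two assumptions underlie this. Patients are taken to receive the regimen as section 4.1.1 schedules it. The count of six uses that section's own list; section 8.3 describes mycophenolate sodium and basiliximab, which are not on it, and does not discuss rituximab, so the two sections must be reconciled.

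**What to change.** 1. In the synopsis, section 2.1 and section 6.1, restate the objective as the safety and efficacy of CABG plus intramyocardial cell injection with perioperative immunosuppression, compared with CABG alone.
2. Reconcile the synopsis description of the cell arm with section 3, so that the immunosuppression appears in both.
3. In section 6.5.3, present adverse events by arm, split by onset during or after the immunosuppression period, with the control arm divided at the same postoperative days. Keep laboratory data by visit, because a fixed cut at POD28 would run through the M1 window. Show the day of onset as well, since section 8.2.1 places most acute GvHD between days 20 and 40, which straddles the cut. The detail may go into the analysis plan if section 6.5.3 points to it.
4. State in section 6.5.3 that early between-arm differences cannot be assigned to the cells alone or to the drugs alone.

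Before the period is defined, two further sets of passages must be reconciled. Section 4.1.1 starts cell-arm drugs on preoperative days 3 and 1, while section 6.4 reveals the allocation immediately before surgery and Table 3 begins adverse event collection on D0.

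The cost is wording in a few places, one extra table split and a narrower claim than that the cell injection itself is safe and effective. No change of treatment is involved.
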